7.3.5. Analyses of serious adverse events

The cumulative incidence rates (per 100 subjects) of serious adverse events (SAEs) within the study period will be estimated by Vaccine group, with 95%CI, for the Cumulative vaccinated cohort Weeks 35-48.

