3. STUDY DESIGN

3.1. Study design overview

- Type of design: prospective post-authorisation passive enhanced safety surveillance study in the United Kingdom (UK).
- Co-Sponsors: GSK and the University of Surrey, Guildford UK.
- Study vaccination period: intended to be from 01SEP2017 (start of the seasonal influenza vaccination) up to 30NOV2017.
- Study period: intended to be from 01SEP2017 (start of the seasonal influenza vaccination) up to 7 days after last study participant vaccinated.
- Study General Practitioner (GP) practices: 10 GP practices ordering mainly GSK's Fluarix Tetra vaccine for the 2017/18 season will be enrolled in the study before the start of the seasonal influenza immunisation season. These 10 GP practices will be selected based on their willingness to participate, their location (distributed across England (in London, a Northern city, and rural settings in the North and South)) and that the participating population spans different age strata, different levels of deprivation, different ethnic mix, different brand of computerised medical record systems, and different practice sizes. GP practices will also be included based on their ability to comply with the study protocol requirements.
- Study participants: subjects who receive influenza vaccination between 01SEP2017 and 30NOV2017 in the 10 enrolled GP practices and who have not opted-out of data sharing.
- Number of subjects: according to the sample size assumption (conservative approach), it was estimated to be able to reach a number of 50,000 subjects registered in the 10 enrolled GP practices with an estimate of 5,000 vaccinated subjects with 7 days of follow-up after vaccination.
- **Type of study:** self-contained.

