4. OBJECTIVES

The eligible study period is expected to be from 01 September until 30 November 2017.

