6.4. Cumulative vaccinated cohorts

The Cumulative vaccinated cohorts (for each ISO Week 35 to 48, denoted as Weeks 35-35 to Weeks 35-48) will include all subjects from the Total eligible registered population

- who are vaccinated with a seasonal influenza vaccine at any point from study start up (i.e. 01SEP2017) up to the end of the week of interest (i.e. cumulatively since the beginning of the study)
- who are registered in EHR during the safety follow-up period (from vaccination up to 7 days post vaccination)

For example, the Cumulative vaccinated cohort Weeks 35-40 will include all subjects from the Total eligible registered population:

- who are vaccinated with a seasonal influenza vaccine at any point from study start up (i.e. 01SEP2017) up to the end of Week 40 (i.e. cumulatively since the beginning of the study)
- who are registered in EHR during the safety follow-up period (from vaccination up to 7 days post vaccination)

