7.3.2. Analyses of primary objectives

The weekly incidence rate (per 100 subjects) of any AEIs within 7 days* post-vaccination period reported via ADR card will be estimated by Vaccine group as follows in the Weekly vaccinated cohorts restricted to subjects who received the ADR card:

- The denominator will be the number of subjects in the Weekly vaccinated cohort for the week of interest who received the ADR card
- The numerator will be the number of subjects from the denominator who reported any AEIs on the ADR card within 7 days following vaccination with the seasonal influenza vaccine

**Day of vaccination plus the following 7 days*

The cumulative incidence rate (per 100 subjects) of any AEIs within 7 days post-vaccination period reported via ADR card will be estimated by Vaccine group as follows in the Cumulative vaccinated cohorts restricted to subjects who received the ADR card:

- The denominator will be the number of subjects in the Cumulative vaccinated cohort up to the week of interest who received the ADR card
- The numerator will be the number of subjects from the denominator who reported any AEIs on the ADR card within 7 days following vaccination with the seasonal influenza vaccine

Similarly, weekly and cumulative incidence rates will be estimated for the following AEIs within 7 days post-vaccination period reported via ADR card:

- Fever/pyrexia
- Fever $>38.5^{\circ}\text{C}$ and $>39.5^{\circ}\text{C}$ (with a temperature measurement recorded in EHR; independent of route of measurement)
- Local symptoms (i.e. local erythema)
- Any and each general non-specific symptom: drowsiness, fatigue, headache, irritability and malaise
- Any and each respiratory AE: conjunctivitis, coryza, cough, epistaxis, hoarseness, nasal congestion, oropharyngeal pain, rhinorrhoea, wheezing
- Any and each gastrointestinal AE: decreased appetite, diarrhea, nausea, vomiting
- Any and each sensitivity/anaphylaxis AE: anaphylactic reactions, facial oedema, hypersensitivity reactions
- Rash
- Any and each musculoskeletal AE: arthropathy, muscle aches / myalgia
- Any and each neurological AE: Bell's palsy, Guillain-Barre syndrome, peripheral tremor, seizure / febrile convulsions

Similarly, weekly and cumulative incidence rates of any SAEs within 7 days post-vaccination period reported via ADR card will also be generated.

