In addition, weekly and cumulative incidence rates of any AEIs, each AEIs category (i.e. fever/pyrexia, local symptoms, any general non-specific symptom, any respiratory, any gastrointestinal, any sensitivity/anaphylaxis, rash, any musculoskeletal and any neurological AEs) and SAEs within 7 days post-vaccination period reported via ADR card will also be generated by Age group (6 months to 5 years; 6 to 12 years; 13 to 17 years; 18-65 years; >65 years) and by UK CMO-specified risk status (at risk, not at risk).

95% confidence interval (CI) adjusted for clustering effect of GP practices will be computed on all estimated incidence rates (Clopper-Pearson exact CI modified for cluster data as described in [Annex 1](#)).

The design effects and the intra-cluster correlation coefficients will also be estimated as described in [Annex 1](#) for the estimated cumulative incidence rates of AEIs reported on the ADR card within the 7 days post-vaccination period for the Cumulative vaccinated cohort Weeks 35-48 restricted to subjects who received the ADR card.

7.3.3. **Analyses of secondary objectives**

All analyses described for the primary objectives (refer to Section [7.3.2](#)) will also be generated by Vaccine group for all subjects included in the Weekly vaccinated cohorts and the Cumulative vaccinated cohorts (i.e. whether or not they received the ADR card).

For the weekly incidence rates (per 100 subjects):

- The denominator will be the number of subjects in the Weekly vaccinated cohort for the week of interest
- The numerator will be the number of subjects from the denominator who reported the specified AEI within 7 days following vaccination with the seasonal influenza vaccine using data entered in the EHR (i.e. AEIs derived from ADR card and medically attended AEIs)

For the cumulative incidence rates (per 100 subjects):

- The denominator will be the number of subjects in the Cumulative vaccinated cohort up to the week of interest
- The numerator will be the number of subjects from the denominator who reported the specified AEI within 7 days following vaccination with the seasonal influenza vaccine using data entered in the EHR (i.e. AEIs derived from ADR card and medically attended AEIs)

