12.2. Data derivation

12.2.1. Date derivation

The date of birth will be modified during the extract from EHR to protect personally identifiable information. The modified date of birth will contain the exact month and year of birth of the subjects, but the exact day of birth will not be provided and will be set to '01' for all the subject's birth dates.

If the vaccine administration date is incomplete or missing the following rule will be applied:

- Day missing: 15 is used (standard GSK imputation)
- Month or year is missing: vaccination not included in the statistical analysis

If the start date of the AEI is incomplete or missing, a conservative approach (worst case scenario) will be used for imputation for the vaccinated subjects. The rules for imputation are detailed below, the examples are given assuming 16OCT2017 as date of vaccine administration.

- Day missing:
 - Month of onset = month of administration: day of administration will be used (e.g. OCT2017 → 16OCT2017)
 - Month of onset > month of administration: first day of the month will be used (e.g. NOV2017 → 01NOV2017)
 - Month of onset < month of administration: AEI not included in the statistical analysis
- Month or year missing: AEI not included in the statistical analysis

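### SAP 7.3.5 gives SAEs over the whole study period as a proportion of vaccinees; counted from vaccination, follow-up runs from 97 down to 7 days, so the figure depends on vaccination date

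*SAP*

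**What the plan says.** SAP 7.3.5 reads: "The cumulative incidence rates (per 100 subjects) of serious adverse events (SAEs) within the study period will be estimated by Vaccine group", with a 95% CI, for the Cumulative vaccinated cohort Weeks 35-48. It defines no numerator beyond this and states no window measured from each subject's vaccination.

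The SAP defines the study period in section 3.1: "intended to be from 01SEP2017 (start of the seasonal influenza vaccination) up to 7 days after last study participant vaccinated". The same section lists the vaccination period separately, as 1 September to 30 November 2017.

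The other AEI and SAE rates in the final analysis (SAP 7.3.2, 7.3.3, 7.3.6 and 7.3.7) use a 7-day post-vaccination window, which 7.3.2 explains as "Day of vaccination plus the following 7 days". Seven-day SAE rates are already planned. In 7.3.2, "weekly and cumulative incidence rates of any SAEs within 7 days post-vaccination period reported via ADR card will also be generated". In 7.3.3 the same analyses "will also be generated by Vaccine group for all subjects included in the Weekly vaccinated cohorts and the Cumulative vaccinated cohorts", whether or not the subject received a card.

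The cohort rule in SAP 6.4 admits subjects "who are registered in EHR during the safety follow-up period (from vaccination up to 7 days post vaccination"). Annex 1 (SAP 12.1) describes confidence intervals for proportions only.

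**The concern.** A proportion of vaccinees with an event can be interpreted only if each vaccinee had a known, preferably equal, time in which the event could count. SAP 7.3.5 uses a calendar period instead. Early vaccinees then contribute months of follow-up and late vaccinees about a week, yet each counts as one subject in the denominator.

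Three things follow:

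- The figure cannot be set beside the 7-day SAE rates in the same report, because it covers a different and variable length of time.
- The figure is tabulated by vaccine group with intervals, so readers will compare groups. If one brand was given earlier in the season, its proportion would be higher from background SAEs alone.
- The section does not require onset after vaccination. Taken at its word, it would attribute to vaccinees SAEs that occurred before their vaccination.

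**Working it through.** The plan gives no follow-up length or expected SAE rate for 7.3.5, so there is no figure to reproduce. The check is calendar arithmetic.

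**Inputs.** Vaccination dates run from 1 September to 30 November 2017 (SAP 3.1 and Annex 4). Study end is the last vaccination plus 7 days (SAP 3.1). If the last vaccination is on 30 November, study end is 7 December 2017.

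**Reading 1: SAEs counted from vaccination.** Potential follow-up = study end minus vaccination date.

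- 1 September: 29 + 31 + 30 + 7 = 97 days.
- 16 October (the example date in SAP 12.2.1): 15 + 30 + 7 = 52 days.
- 30 November: 7 days.

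Averaged over the dates in selected Annex 4 weeks:

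| Week of vaccination | Follow-up by date (days) | Mean (days) |
|---|---|---|
| 35 (1-3 Sep) | 97 to 95 | 96 |
| 39 (25 Sep-1 Oct) | 73 to 67 | 70 |
| 44 (30 Oct-5 Nov) | 38 to 32 | 35 |
| 48 (27-30 Nov) | 10 to 7 | 8.5 |

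A week 39 vaccinee has twice the follow-up of a week 44 vaccinee (70/35). The 7-day window in 7.3.2 includes the day of vaccination, so it spans 8 calendar days. On that convention the 7.3.5 range is 98 to 8 days, and only subjects vaccinated on the last date have the same window in both analyses.

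**What this does to a proportion (assumption, for illustration only).** Suppose a constant background SAE risk h per 30 days, with h from 0.1% to 2%. The documents give no such figure. The expected proportion after t days is 1 - (1 - h)^(t/30).

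- t = 97: 0.32 per 100 (h = 0.1%) to 6.32 per 100 (h = 2%).
- t = 7: 0.02 to 0.47 per 100.
- Ratio: 13.8 at h = 0.1% and 13.5 at h = 2%.

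This contrasts the first and last vaccination dates. It is not an estimate of any difference between vaccine groups.

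**Check on the fix.** At h = 0.1%, per person-time, the first-day figure is 0.323 x 30/97 = 0.10 per 100 per 30 days. The last-day figure is 0.0233 x 30/7 = 0.10. The dependence on vaccination date through follow-up length disappears.

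**Reading 2: SAEs counted anywhere in the calendar period.** Everyone then has the same 97 days and the proportion does not vary with vaccination date through follow-up length. But a subject vaccinated on 30 November contributes 90 days before vaccination (1 September to 30 November) and 7 after. The only text pointing the other way is in SAP 12.2.1: "Month of onset < month of administration: AEI not included in the statistical analysis". That rule covers AEIs with an incomplete onset date and does not govern 7.3.5 in general.

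Under either reading the figure does not measure SAE occurrence over a defined time after vaccination.

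**The case against.** The strongest reply is that little depends on this table. Seven-day SAE rates by vaccine group are planned for card recipients and for all vaccinees. No objective or endpoint in SAP 4 and 5 is an SAE rate. SAP 8 makes all analyses descriptive, and SAP 3.1 calls the study self-contained. For rare SAEs, sampling error may exceed any timing effect: protocol Table 1 gives a relative standard error of 44.7% at 0.10% with 5,000 vaccinees. All of this stands, and it limits the severity. It does not supply the missing time basis.

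It can also be said that the cohort rule implies 7 days. It does not: the rule fixes who enters the cohort, not which SAEs count. If 7 days were meant, 7.3.5 would repeat 7.3.3. A footnote in the separate tables annex (SAP 1 and 11) might state a window. That annex is not among the documents, and the SAP text should stand without it.

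Two stronger readings are tempting, and the documents support neither.

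- SAP 4 says: "The eligible study period is expected to be from 01 September until 30 November 2017". A reader might infer that observation stops on 30 November, which would give 90 to 0 days and shorten even the 7-day window for subjects vaccinated on 24-30 November. The protocol's inclusion criteria use eligibility for people vaccinated between those dates, so the sentence most naturally means the vaccination window. The other reading would also conflict with SAP 3.1, 6.3 and 6.4.
- A reader might infer that the comparison between vaccine groups is biased. That would need vaccination timing by brand, which the documents do not give. With equal timing there is no distortion from this source.

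**Conclusion.** The point holds as a minor one. If SAEs are counted from vaccination, which is the sensible reading but is not stated, the SAP 3.1 study period gives 97 to 7 days of potential follow-up. The 7.3.5 proportion then mixes unequal follow-up and is not comparable with the 7-day SAE rates. Between vaccine groups, it is comparable only if vaccination timing is similar; size and direction are otherwise unknown. If the section is taken literally, the fault is instead that SAEs before vaccination count.

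The range assumes vaccinations on both 1 September and 30 November, and registration to study end. Registration is required only to day 7, so actual follow-up may be shorter for subjects who leave. The primary and secondary analyses, the cohorts and the sample size are unaffected.

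**What to change.** In SAP 7.3.5:

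1. State that the study period is the one defined in SAP 3.1, and count only SAEs with onset on or after vaccination up to that end date.
2. Report them per person-time from vaccination, censored at the end of registration where known. Name a confidence interval for rates, because Annex 1 covers proportions only; to match the rest of the SAP it should allow for clustering by practice.
3. If person-time is not feasible, report a count of these SAEs with the follow-up range, and use the 7-day rates in 7.3.3 as the only SAE rate by vaccine group.
4. Under either option, note that the result is not comparable with the 7-day rates.

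The cost is small. Vaccination dates are already extracted. The extraction lists (protocol, data extraction section; SAP 3.4) name date of registration but no end date, so censoring may be only partial. The cohort rule does already require registration status to be known up to day 7. Person-time adds one interval method and a little programming. The count option gives up any rate for SAEs after day 7. Simply deleting 7.3.5 is less attractive, since it is the only planned analysis that gives a rate covering those later SAEs.

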7.3.6. Sensitivity analyses

7.3.6.1. Not accounting for clustering effect

To assess the impact of cluster data on the estimated 95%CI, the 95%CI will also be computed for the incidence rates described below using the Clopper-Pearson exact CI method not taken into account the clustering effect.

The cumulative incidence rates (per 100 subjects) of each AEIs within the 7 days post-vaccination period reported via ADR card, with exact 95%CI not accounting for cluster effect of GP practices (Clopper-Pearson exact CI method as described in [Annex 1](#)), will be estimated by Vaccine group for the Cumulative vaccinated cohort Weeks 35-48 restricted to subjects who returned the ADR card.

The cumulative incidence rates (per 100 subjects) of each AEIs within the 7 days post-vaccination period using data entered in the EHR (i.e. AEIs derived from ADR card and medically attended AEIs), with exact 95%CI not accounting for cluster effect of GP practices (Clopper-Pearson exact CI method as described in [Annex 1](#)), will be estimated by Vaccine group for the Cumulative vaccinated cohort Weeks 35-48.

7.3.6.2. Subjects who returned the ADR card

The cumulative incidence rates (per 100 subjects) of each AEIs within the 7 days post-vaccination period reported via ADR card, with 95%CI, will be estimated by Vaccine group for the Cumulative vaccinated cohort Weeks 35-48 restricted to subjects who returned the ADR card:

- The denominator will be the number of subjects in the Cumulative vaccinated cohort Weeks 35-48 who returned the ADR card
- The numerator will be the number of subjects from the denominator who reported the AEI on the ADR card within 7 days following vaccination with the seasonal influenza vaccine

7.3.7. Analysis on the RCGP RSC network of practices

The Royal College of General Practitioners Research and Surveillance Centre (RCGP RSC) network of practices includes approximately 170 GP practices.

The RCGP RSC network will be used to observe the trend of AEI rates using a larger sample of GPs.

The 2017 RSCGP RSC vaccinated cohort will include all subjects from the RSCGP RSC population

- who have not opted-out of data sharing
- who will be vaccinated against influenza at any point during the study vaccination period
- who have a valid NHS number recorded in EHR
- with date of birth recorded in EHR
- with gender recorded in EHR
- who are registered in EHR during the 7 days post vaccination period

The cumulative incidence rate (per 100 subjects) of each AEI within the 7 days post-vaccination period, with 95%CI, will be estimated by Vaccine group as follows:

- The denominator will be the number of subjects from the 2017 RCGP RSC vaccinated cohort
- The numerator will be the number of subjects from the denominator who reported the specified AEI during the 7 days following vaccination with the seasonal influenza vaccine using data entered in the EHR

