Bias: Any disparities in the data generated compared with the national population and the immunisation recommendations in the UK will be discussed.

Study size: As per EMA requirement and Vaccine Working Party (VWP) recommendations, a target of at least 1000 vaccinees across all age groups (6 months to 5 years; 6 to 12 years; 13 to 17 years; ≥18-65 years; >65 years). The sample size proposed in this study accounts for the probability of observing at least one event in the 10 enrolled GP practices together with the level of precision associated with the finding.

Statistical methods: Weekly and cumulative incidence rates of AEIs within 7 days following vaccination with a seasonal influenza vaccine (GSK's *Fluarix Tetra* or another influenza vaccine) will be estimated, with 95% confidence intervals (CIs).

Outputs:

Weekly analysis: A weekly analysis of influenza vaccination and uptake by vaccine brand, different age and at-risk (as per UK CMO recommendations) groups and reports of AEIs in vaccinees will be produced. Those reported at consultations in the practice (medically attended) as well as those reported through ADR cards will be listed.

Final analysis: Interim weekly safety reports and a final comprehensive study report at the end of observation period will be produced. The findings will be discussed in light of the rates of adverse reactions observed in the RCGP network, in clinical trials performed with GSK's seasonal influenza vaccines and, as appropriate, with rates observed in EPI-FLU-045 and EPI-FLU-046 studies.

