5. RESEARCH METHODS

a. Study Design

Study setting and population

Routinely collected primary care data from up to ten GP practices will be extracted, to support passive surveillance. Additionally, this passive surveillance will be enhanced by the use of a card-based ADR reporting system. ADR card will be distributed to patients and upon return entered into the EHR system.

EPI-FLU-055 VS UK study targets to follow vaccinated patients between 01/09/2017 and 30/11/2017.

A customized ADR card will be used, which lists pre-defined categories of AEIs to be reported, similarly to study EPI-FLU-046 (2016/2017 season). A field will also be included to report AEIs not listed as well as a field to indicate that no AEI occurred within the 7 days-time window. Patients will be provided with the ADR cards and asked to complete the ADR cards with any AEIs occurring within 7 days post vaccination and to return the cards to the GP practices not later than 14 days post-vaccination^{vii}.

GP practices ordering mainly GSK's *Fluarix Tetra* vaccine for the 2017/18 season will be contacted to inquire about their interest in participating in this study. This may also include existing research contacts and networks of the University of Surrey. GP practices selection will ensure distributed location across England (in London, a Northern city, and rural settings in the North and South) and that the participating population spans different age strata, different levels of deprivation, different ethnic mix, different brand of computerised medical record systems, and different practice sizes. However, this will be tempered by our need to recruit before the start of the influenza immunisation season.

GP practices will also be included based on their ability to comply with the protocol requirements (e.g., number of subjects registered, IT system used). GP practices will be reimbursed for their involvement in this study, according to the National Institute of Health Research (NIHR) guidelines for industry sponsored studies^{viii}.

Of note, regulatory compliance studies can be registered with the National Institute for Health Research (NIHR) Clinical Research Network (CRN) Portfolio^{viii}. Advice will be sought as to whether this study qualifies.

Inclusion criteria

1. Surveillance is planned to apply to vaccination between 1st September and 30th November 2017

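### The RCGP RSC network cohort in SAP 7.3.7 does not exclude the 10 enrolled practices, so card-solicited AEIs would enter the network rate if any of them are network members

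*SAP*

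**What the plan says.** **Cohort.** SAP 7.3.7 describes a "network of practices includes approximately 170 GP practices" and builds its cohort broadly: "The 2017 RSCGP RSC vaccinated cohort will include all subjects from the RSCGP RSC population". Six conditions follow: no opt-out, vaccination in the study period, a valid NHS number, date of birth, gender, and registration during the 7 days after vaccination. None refers to the enrolled practices. The corresponding paragraph in the Protocol, under its sensitivity analyses, has no exclusion either.

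**Rate.** "The denominator will be the number of subjects from the 2017 RCGP RSC vaccinated cohort". The numerator counts those who "reported the specified AEI during the 7 days following vaccination with the seasonal influenza vaccine using data entered in the EHR". For the study cohorts, SAP 7.3.3 spells out what EHR data means: "using data entered in the EHR (i.e. AEIs derived from ADR card and medically attended AEIs". Protocol 5a (data extraction and data management) confirms that returned cards are coded into the same EHR.

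**Use.** The Protocol synopsis, under the final analysis, says: "The findings will be discussed in light of the rates of adverse reactions observed in the RCGP network". Clinical trials and the two earlier pilot studies are named there as further context. SAP 7.3.7 gives a narrower purpose: observing the trend of AEI rates in a larger sample.

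**Possible overlap.** Protocol 4a places the network's data and analysis hub at the University of Surrey. On recruitment, Protocol 5a says: "This may also include existing research contacts and networks of the University of Surrey". SAP 3.1 says that "10 GP practices ordering mainly GSK's Fluarix Tetra vaccine for the 2017/18 season will be enrolled in the study".

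**The concern.** Enrolled practices hand out a card listing specific symptoms and code what comes back. Other network practices record only what reaches them in routine care. If an enrolled practice is also a network member, SAP 7.3.7 as written counts its vaccinees in the network denominator and its card-reported events in the network numerator. The network rate then depends partly on how the study was run, and the same subjects appear in both the study rate and the rate used as context for it.

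The Fluarix Tetra column is the most exposed. SAP 7.3.7 reports the network rate by Vaccine group, and the enrolled practices are chosen because they mainly order that brand. Their share of the network's Fluarix Tetra vaccinees may therefore be well above their share of practices. A brand difference within the network table could then reflect where cards were issued.

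**Working it through.** The documents give neither the overlap nor an expected network rate, so there is no plan figure to reproduce. The calculation shows how large the effect could be.

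**Inputs from the documents**
- Enrolled practices: 10 (SAP 3.1).
- Network practices: about 170 (SAP 7.3.7).

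**Assumptions, not in the documents**
- Equal numbers of vaccinees per practice.
- Routine-only rate r = 1%.
- Card-plus-routine rate R = 3%, 5% or 10%. All these rates lie inside the 0.01% to 20% range used in the Protocol's sample size section. That R exceeds r is plausible because cards solicit events and, per Protocol 4a, return reached about 50% in the previous season.
- Number of enrolled practices that are network members: k = 0, 1, 5 or 10.

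**All vaccines combined**

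Weight of the overlapping practices: w = k/170.

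Network rate = r + w × (R − r).

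Example with k = 10 and R = 10%: w = 10/170 = 5.9%; rate = 1% + 0.0588 × 9% = 1.53%.

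| k | w | R = 3% | R = 5% | R = 10% |
|---|---|---|---|---|
| 0 | 0% | 1.00% | 1.00% | 1.00% |
| 1 | 0.6% | 1.01% | 1.02% | 1.05% |
| 5 | 2.9% | 1.06% | 1.12% | 1.26% |
| 10 | 5.9% | 1.12% | 1.24% | 1.53% |

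The direction follows from the formula: whenever R exceeds r, the network rate moves towards the study rate and closes a fraction w of the gap.

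**Fluarix Tetra group**

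Let s1 and s2 be the Fluarix Tetra shares of vaccinees in enrolled and other network practices. Then w = k·s1 / [k·s1 + (170 − k)·s2], which exceeds k/170 whenever s1 exceeds s2. Assume s1 = 80% and s2 between 40% and 5%.

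- k = 1: w = 0.8/(0.8 + 67.6) = 1.2%, up to 0.8/(0.8 + 8.45) = 8.6%.
- k = 10: w = 8/(8 + 64) = 11%, up to 8/(8 + 8) = 50%.

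With r = 1% and R = 3% to 10%, the network Fluarix Tetra rate for k = 10 is 1.22% to 2.00% when w = 11% (1% + 0.111 × 2% or 9%), and 2.00% to 5.50% when w = 50% (1% + 0.5 × 2% or 9%). These figures need full overlap and assumed brand shares, so they show sensitivity and are not a forecast.

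**After exclusion**, w = 0 and the rate is r in every scenario.

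**The case against.** **Overlap is not shown.** No text available here says that any enrolled practice is a network member. The main recruitment route is practices ordering mainly Fluarix Tetra, and the sentence on the university's contacts and networks does not name the RCGP RSC. The practice-selection flow chart and the separate tables document could not be seen and might settle it. This stands, and it is why the point is conditional.

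**Inclusion may be intended.** A larger sample of practices can reasonably include the enrolled ones. A reader might infer that the network is meant as a routine-recording reference drawn from other practices, but neither document says so. What remains is that the SAP does not state which was meant.

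**A reader might infer that overlap would make the comparison falsely reassuring.** The example does not support that. The gap between 1% and 3% to 10% is assumed to come from soliciting events by card, so shrinking it does not hide a safety excess. Even at 10% against 1% with ten members, the ratio falls from 10 to about 6.5 (10/1.53), still a large difference.

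**Non-independence has no inferential cost here.** SAP sections 8 and 9.2 state that all analyses are descriptive and that no hypothesis is tested. No contrast or signal threshold using the network rate is planned. This also stands.

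**Card entries carry their own code,** so they could be filtered out. That is true under SAP 3.3.2, but SAP 7.3.7 applies no such filter. Enrolled practices also work from a preferred code list and the Protocol appends a coding-feedback sample, which may change their routine recording as well.

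**Conclusion.** The point holds conditionally. Followed as written, SAP 7.3.7 mixes card-solicited AEIs into the network rate if any enrolled practice is a network member and cards raise recorded AEIs. The documents make overlap possible but do not establish it.

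The size runs from zero to modest for all vaccines combined. A reader might take the full-overlap inflation of 12% to 53% as the expected bias, but it requires all ten practices to be members as well as the assumed rates; with one member it is about 1% to 5%. The Fluarix Tetra group is probably more exposed, by an amount the documents do not allow to be fixed.

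The consequence is limited to one supporting descriptive table and the discussion that draws on it. The point is worth raising because the rule is explicit and correcting it is nearly free.

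**What to change.** Add one criterion to the 2017 RCGP RSC vaccinated cohort in SAP 7.3.7: *who are not registered in one of the 10 enrolled GP practices*. Report how many enrolled practices were removed. If the larger sample was meant to include them, say so and show the network rate, by Vaccine group, with and without them.

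The cost is one SAP line and a filter on practice code. At most 10 of about 170 practices (5.9%) leave the cohort, and nothing changes if there is no overlap. The SAP is dated 11 December 2017, after the planned vaccination period, so membership should be ascertainable.

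Exclusion does not make a card-enhanced study rate like-for-like with a routine network rate. If that contrast is to be discussed, the card code allows a rate limited to medically attended AEIs to be shown for the enrolled practices beside the network rate.
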